## Study Design

### 1. Total number of subjects to be enrolled at this site (enter -1 for chart reviews, banking, registries):

25

### 2. Describe and explain the study design:

This experimental study uses a within-subjects design.

All enrolled participants will be implanted with sEEG electrodes in the auditory cortex based on clinical necessity. During the post-operative period, patients will complete self-paced blocks of trial stimuli by listening to sound via earphones and making behavioral, categorical decisions about speech sounds, duration of stimuli, and pitch of stimuli. Simultaneous sEEG and scalp EEG recordings will be obtained to record neural responses to stimuli.

Participants will first complete a block of stimuli for clear speech to establish a baseline. They will then complete blocks of stimuli with experimental manipulations. All blocks will consist of intermixed exposure trials and test stimuli. Each participant will complete all tasks provided they are willing to do so and that their medical status permits.

Auditory stimuli used in this part of the study are part of the dimension-based statistical learning (DBSL) paradigm developed and extensively tested by [name] in previous research.

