All potential subjects will be patients of [name] and the CHP neurological surgery service, who will decide when and if the patient is medically able to participate in research activities. All research-specific activities will be stopped at the request of the patient, patient's parents, or medical team. It will be made clear to patients and parents that participation is entirely voluntary and that patients or parents may make the decision to discontinue involvement in the study at any time.

Prior to completing research activities described below, participants will complete a 5-minute hearing screening via headphones by providing click responses on a computer. The hearing screening will be completed remotely within the participant's home and will be hosted and accessed on the Gorilla experiment platform ([gorilla.sc](http://gorilla.sc)). The research team will meet briefly with participants via Zoom on a non-recorded video call to provide instructions and guidance on accessing and completing the screening. Participant responses will be recorded directly and saved in a database on the Gorilla platform. This screening will occur prior to sEEG implantation.

Participants will also participate in a brief (~12-15 minute) language screening that evaluates phonological awareness. Participants will listen to single-word or single-letter speech stimuli played from a laptop, and provide verbal responses that require them to add, subtract, or blend sounds within a word. This screening procedure will occur in-patient following sEEG implantation but prior to the activities described below which involve neural recordings.

Neither screening procedure will be used for the purposes of determining eligibility.

Each participant will complete self-paced blocks of stimuli that will first establish a baseline for neural activity and behavioral responses with clear speech, and will then record responses for experimentally manipulated blocks to introduce 1) speech-in-noise and 2) a Canonical-Reverse block to model an "accent." Each block involves listening to sound via earphones and making a categorical decision between initial consonants (/b/ or /p/) by tapping a button to indicate the word heard by the participant.

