All auditory stimuli will be adjusted to a comfortable level for each participant as determined by a calibration process completed by the participant. The blocks can be completed with breaks in between as needed or desired and can occur over the course of the participant's clinical stay in the EMU. All blocks involves listening to sound via earphones and making a categorical decision. Because participation is self-paced, the number of sessions in a day over the total course of an individual's participation will depend on their schedule, health, and motivation to complete research tasks. This period may be up to 10 days, however the patient participant's inpatient stay will not be extended for research purposes.

sEEG electrodes and scalp EEG electrodes will be connected to the study team's recording system before beginning research tasks in order to collect neural recordings specifically for research. The recording system will be disconnected at the completion of each research session. sEEG electrodes will be connected to the EMU's recording system for the duration of each participant's inpatient stay per standard of care.

The study team's recording equipment consists of the software required to present stimuli on MATLAB and record electrical signals from electrodes as well as behavioral responses from subjects. Therefore, no audio or visual recordings will be taken.

The risks and benefits of clinical procedures that are part of the patient's standard of care will be explained in a consent process separate from research activities. Electrode placement and recording are conducted strictly based on a patient's clinical needs and will not be dictated or manipulated by research. Participants will incur minimal additional risk by participating in the behavioral research task. Any risks involved will be explained and documented in the informed consent process and may include fatigue, boredom, or frustration. Research staff will ensure that participants and parents/guardians are aware that participation is entirely voluntary and may stop at any time. Every effort will be made to ensure patient comfort throughout study procedures.

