To characterize shifts in neural encoding across listening contexts, we will investigate Noise using encoding models and Canonical/Reverse contexts using *cluster-based approaches*.^{32,49} Encoding models will be built from the Noise context for all channels and timepoints, using the same approach as Baseline. If a channel/timepoint is significant in either Baseline or Noise, the F0 and VOT coefficient *t*-statistics will be compared across contexts. We hypothesize that encoding of F0 will strengthen and VOT will weaken in Noise, as measured by changes in *t*-statistic magnitudes across multiple models. Next, we will compare neural responses for each of the two *Test* stimuli (which were embedded in the F0 x VOT grids, **Figure 1a**) between Baseline vs. Canonical and Canonical vs. Reverse. The clustering approach will look only at Baseline significant channels and time windows and involves randomly assigning listening context labels to single-trial data followed by a *t*-test at each time step. Across all permutations, a criterion value will be established for each timepoint (>95% of absolute value of *t*). For each of these permutations, we will next determine whether its value exceeds criterion across timepoints, and for how many timepoints it exceeds criterion (a 'cluster'). For each cluster, *t* values will be summed and assigned to all points in the cluster, with the largest summed cluster value stored for each permutation. This will create a null distribution of 1000 cluster values. We then will establish whether the cluster size calculated across real neural data (organized according to listening context) exceeds the 95% permutation-based cluster values such that $p < .001$ indicates an observed cluster is greater than all permutation-based clusters. Using this approach, we will identify context-dependent shifts in HGA responses, which we predict will reflect observed shifts in perceptual weights. Namely, we hypothesize that HGA responses in F0-encoding channels will be enhanced in the Canonical context relative to both Baseline and the Reverse context.

Rigor and Reproducibility. Analyses will be controlled for multiple comparisons, with sex as a co-variate in our analyses. We will use pre-registration and provide access to all the deidentified source data.

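### The Canonical contrasts shuffle single-trial context labels across blocks recorded at different times, so a shift in response level between blocks can be declared a listening-context effect

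*Protocol*

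**What the plan says.** **Order of contexts.** Protocol, Study Design item 2: "Participants will first complete a block of stimuli for clear speech to establish a baseline". Of what follows it says only "They will then complete blocks of stimuli with experimental manipulations". Research Activities item 1 lists the manipulations as "1) speech-in-noise and 2) a Canonical-Reverse block". Neither document mentions randomising, counterbalancing, repeating or alternating contexts, or says whether Canonical or Reverse comes first.

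**What is mixed within a block.** "All blocks will consist of intermixed exposure trials and test stimuli". This mixes trial types; it does not mix contexts.

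**Spacing.** Research Activities item 1: "The blocks can be completed with breaks in between as needed or desired", and the blocks "can occur over the course of the participant's clinical stay in the EMU", a period of up to 10 days. The research recording system is disconnected after each session.

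**The test.** In the SAP's neural analyses, the cluster approach compares Baseline with Canonical and Canonical with Reverse. It does so for each of the two Test stimuli, at channels and time windows that were significant at Baseline. Its null comes from "randomly assigning listening context labels to single-trial data", with 1000 permutations. The shuffle is not restricted by block or session, and there is no time or order term. Sex is the only covariate named.

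**The predictions.** Earlier in the same section the SAP predicts better differentiation between the two F0-differentiated Test stimuli in Canonical than in Reverse, and in Canonical than in Baseline. That is a statement about a difference between stimuli. The cluster test examines each stimulus alone.

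**The concern.** A label-permutation test is valid when, with no effect, the labels could have fallen on any of the trials. Here trials from different contexts are recorded at different times, possibly in different sessions. If signal level, vigilance or habituation changes between those times, trials within a context resemble one another more than trials across contexts, even when context does nothing. Shuffling single trials ignores this, so the null distribution is too narrow.

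Testing each stimulus alone makes matters worse. A shift that affects both stimuli equally, and so says nothing about F0 weighting, does not cancel.

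These two contrasts carry the neural evidence on the accent manipulation (H4 and H5), and the claims about where in the cortical hierarchy such plasticity appears (H6 and H7) draw on them too. A drifting electrode could be reported as one that shows context-dependent plasticity.

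**Working it through.** **The plan's own figure.** The SAP gives no error rate for the cluster test. Its N=25 rests on pilot effect sizes shown in a figure and cannot be reproduced from the text. At 80% power and two-sided 0.05, a paired t-test with N=25 corresponds to a standardised effect of about 0.58. That is a back-calculation and does not enter below.

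**Inputs.** From the documents: two contrasts, each Test stimulus separately, single-trial labels shuffled, 95% criteria, N=25. Assumed, because the documents do not give them: n = 20 or 40 Test trials per context for one stimulus, and a constant shift d between two blocks of 0 to 0.3 single-trial SD.

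**Step 1, one timepoint.** With no context effect, the standardised difference between blocks has mean d/√(2/n). The two-sided rejection rate is P(Z > 1.96 − d/√(2/n)) + P(Z < −1.96 − d/√(2/n)). For n=40 and d=0.2, d/√(2/n) = 0.2/0.2236 = 0.894, and the rate is P(Z > 1.066) + P(Z < −2.854) = 0.143 + 0.002 = 0.145.

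**Step 2, the SAP's cluster test, one electrode and one stimulus.** Simulated with 40 timepoints, autocorrelation 0.8, 300 permutations and 500 repetitions:

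| Trials per context | d=0 | d=0.1 | d=0.2 | d=0.3 |
|---|---|---|---|---|
| 20 | 0.05 | 0.07 | 0.18 | 0.33 |
| 40 | 0.04 | 0.12 | 0.29 | 0.54 |

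Repeat runs differ by a few percentage points. The test holds its level only with no shift, and more trials make the inflation worse.

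**Step 3, the contrast the SAP predicts.** The same simulation was run on the change between contexts in the high-F0 minus low-F0 difference, with the same shift added to both stimuli. The shift cancels: (high + d) − (low + d) = high − low. The rejection rate is about 5-7%, which is nominal within simulation error.

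**Step 4, what Step 3 does not remove.** A loss of response gain shrinks the F0 difference itself. If that difference is 0.4 SD and gain falls 20% from one block to the next (both assumed), the false change is 0.4 × 0.20 = 0.08 SD. Only order control addresses this.

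**Step 5, order control at patient level.** Take N=25, a mean order shift of 0.2, a between-patient SD of that shift of 0.2 (both assumed), and no context effect. A group t-test on one stimulus rejects 73% (n=20) or 89% (n=40) of the time if every patient has the same order. With orders split 13/12 and an order term, it rejects 4.9% and 5.0%. Patient-level inference therefore needs the order list as well.

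**Step 6, permuting whole runs within an electrode.** With k runs per context there are C(2k,k) labelings, so the smallest two-sided p is 2/C(2k,k). For k=2 this is 2/6 = 0.33; for k=4 it is 2/70 = 0.029. Two runs per context can never reach 0.05.

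**The case against.** **The documents do not state a fixed sequence.** A reader might infer that every context is its own block in a set order. Only Baseline's first position is documented. Noise and Canonical-Reverse are merely listed, and Canonical and Reverse share one named block. The detail may sit in the pre-registration or the proposal's Approach section, which are not in the documents. This stands as a limit on wording. It does not rescue the test, because single-trial shuffling is unsafe under any blocked order. For the same reason, a claim that early withdrawals fall mainly on one particular context is not supported.

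**Drift does not mimic the whole hypothesis.** A reader might infer that fading responses would manufacture the predicted pattern. Baseline comes first, so falling gain pushes Canonical below Baseline, against the prediction. It also does not explain stronger F0 with weaker VOT encoding in Noise. It could imitate Canonical above Reverse, but only if Canonical is run first, which is not stated. This stands. Each contrast is nevertheless tested separately, and on absolute t values, so either one can be falsely significant.

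**A larger error rate can be calculated.** With 20% gain loss, a patient-level t-test on the F0 contrast at N=25 would be falsely significant 34-73% of the time (patient SD 0.25 to 0.15). That is not the error rate of the SAP's test, which is within channel and per stimulus, and it presumes Canonical first.

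**Partial safeguards exist.** Control electrodes outside the supratemporal plane may reveal global drift. Normalising each subband to its baseline may remove background offsets if done per block, but the SAP does not say so, and it would not remove habituation of the evoked response. The expected total task time of 2-3 hours also makes long gaps possible rather than certain.

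**Noise is tested differently.** Noise vs. Baseline compares coefficients from separate encoding models. The permutation argument does not apply to it, although order is confounded there too.

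**Conclusion.** The concern holds for the two cluster-based contrasts. Baseline is always first, no order control is stated for the manipulated contexts, and the SAP's shuffle assumes exchangeability that blocked recording does not provide. With 20-40 trials per context and a shift of 0.2-0.3 single-trial SD, the nominal 5% per-stimulus test rejects roughly 18-55% of the time under no context effect.

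The mechanism follows from the text; the size does not. Trial counts, shift and autocorrelation are all assumptions, and with no shift the test is sound. The documents support neither a documented fixed sequence nor a claim that drift alone would yield the full predicted pattern.

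**What to change.** 1. **Test the predicted quantity.** Replace the two per-stimulus tests with the change between contexts in the high-F0 minus low-F0 HGA difference.
2. **Move the confirmatory inference to patients.** Use patient-level contrasts with sign-flipping across patients, and label within-electrode single-trial permutation results as descriptive. If run-level permutation within an electrode is preferred, plan at least four runs per context. Splitting and alternating Canonical and Reverse would change the exposure from which listeners learn the regularity, so that is a design decision and not merely a statistical one.
3. **Control the order that can be controlled.** Keep Baseline first. Assign Canonical-then-Reverse or Reverse-then-Canonical from a pre-set counterbalanced list over patients, and include an order term. This deals with the gain change that item 1 leaves in.
4. **State the remaining limit.** Baseline vs. Canonical stays confounded with order. Only repeating Baseline later would address it, and that adds task time.

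Items 1 to 3, without the run-level option, need a presentation list and SAP wording, with no extra trials. The price is weaker within-electrode significance claims, and carry-over between Canonical and Reverse averaged over two orders of about 12-13 patients each.

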### 3. Provide a description of the following study timelines:

#### Duration of an individual subject's active participation:

Participants will continue to be enrolled in the study for the duration of their sEEG implantation in the EMU. This period of time may range from 3-10 days post-operatively until the participant completes all research tasks, indicates that they would like to disengage from research activities, or is taken back to the operating room for removal of electrodes.

Each participant will have active participation in the study for only the amount of time per day that they voluntarily desire participating. Blocks of stimuli are self-paced and the research team will offer breaks between blocks as needed or requested by the participant.

Based on previous research with similar protocols and stimulus paradigms, we anticipate that a subject may complete all research tasks over a cumulative period of 2-3 hours. This includes equipment setup and removal.

#### Duration anticipated to enroll all subjects:

This is a two year study. Based on historical volume of patients with similar inclusion criteria within PI [name]'s clinical practice, it is anticipated that the desired number of participants (n=25) will be enrolled within the first year. Should enrollment be lower than anticipated after Year 1, the enrollment period will be extended into Year 2.

### 4. List the inclusion criteria:

1. Individuals 15-25 years old and their parent/guardian where applicable
2. Undergoing sEEG placement in the auditory cortex for clinically necessary localization of epileptic foci or language mapping
3. Fluent English speakers
4. Within the normal range on cognitive, speech-language, and hearing tests (as determined by a speech-language pathologist or neuropsychologist prior to surgery)
5. Normal or corrected-to-normal visual acuity
6. Normal hearing acuity in each ear (as determined during a full audiotmetric assessment)
7. No history of autism or ADHD

### 5. List the exclusion criteria:

1. Individuals with intellectual disability
2. Abnormal epileptiform activity in the auditory cortex
3. Lack of fluent English comprehension/production
4. Severe language or auditory specific cognitive dysfunction
5. History of autism or ADHD

## Research Activities

### 1. \* Provide a detailed description of all research activities (including screening and follow-up procedures) that will be performed for the purpose of this research study. This description of activities should be complete and of sufficient detail to permit an assessment of associated risks. [?](#)

The participants in this study will be 15-25 year-olds undergoing stereoelectroencephalography (sEEG) implantation in the STP for clinically necessary localization of epilepsy foci or language mapping. Enrolled participants will not meet any exclusion criteria. The study will only be conducted if the subject's medical condition permits and if the subject is willing to participate and continue.

Personnel performing the research procedures will be suitably trained research staff.

All research activities will take place at UPMC Children's Hospital of Pittsburgh (CHP). After the clinically necessary sEEG electrodes are placed, patients will be monitored in the acute inpatient setting of the epilepsy monitoring unit (EMU). The EMU offers a fully staffed team of clinicians who will ensure the health of the patient. When patients feel well enough, they will be approached with the opportunity to participate in the proposed research by engaging in behavioral tasks and screening assessments. Participants will have up to 64 scalp electrodes placed at the completion of the surgical procedure to obtain scalp EEG recordings for research purposes. Scalp electrodes will come from the study team's own equipment inventory and will be covered by the head dressing applied to all sEEG patients post-operatively. These electrodes will remain on the scalp until the completion of sEEG recording or upon a participant's withdrawal from the study. sEEG and EEG recordings will occur simultaneously during behavioral tasks.

All clinical decisions, including placement of sEEG electrodes, will be made by the patient's clinical team based solely on medical necessity and benefit. [name] will obtain consent for the surgical procedure to implant sEEG electrodes in a separate process after an extensive clinical evaluation to determine medical utility of the surgery and discussion of risks and benefits involved.

All potential subjects will be patients of [name] and the CHP neurological surgery service, who will decide when and if the patient is medically able to participate in research activities. All research-specific activities will be stopped at the request of the patient, patient's parents, or medical team. It will be made clear to patients and parents that participation is entirely voluntary and that patients or parents may make the decision to discontinue involvement in the study at any time.

Prior to completing research activities described below, participants will complete a 5-minute hearing screening via headphones by providing click responses on a computer. The hearing screening will be completed remotely within the participant's home and will be hosted and accessed on the Gorilla experiment platform ([gorilla.sc](http://gorilla.sc)). The research team will meet briefly with participants via Zoom on a non-recorded video call to provide instructions and guidance on accessing and completing the screening. Participant responses will be recorded directly and saved in a database on the Gorilla platform. This screening will occur prior to sEEG implantation.

Participants will also participate in a brief (~12-15 minute) language screening that evaluates phonological awareness. Participants will listen to single-word or single-letter speech stimuli played from a laptop, and provide verbal responses that require them to add, subtract, or blend sounds within a word. This screening procedure will occur in-patient following sEEG implantation but prior to the activities described below which involve neural recordings.

Neither screening procedure will be used for the purposes of determining eligibility.

Each participant will complete self-paced blocks of stimuli that will first establish a baseline for neural activity and behavioral responses with clear speech, and will then record responses for experimentally manipulated blocks to introduce 1) speech-in-noise and 2) a Canonical-Reverse block to model an "accent." Each block involves listening to sound via earphones and making a categorical decision between initial consonants (/b/ or /p/) by tapping a button to indicate the word heard by the participant.

All auditory stimuli will be adjusted to a comfortable level for each participant as determined by a calibration process completed by the participant. The blocks can be completed with breaks in between as needed or desired and can occur over the course of the participant's clinical stay in the EMU. All blocks involves listening to sound via earphones and making a categorical decision. Because participation is self-paced, the number of sessions in a day over the total course of an individual's participation will depend on their schedule, health, and motivation to complete research tasks. This period may be up to 10 days, however the patient participant's inpatient stay will not be extended for research purposes.

sEEG electrodes and scalp EEG electrodes will be connected to the study team's recording system before beginning research tasks in order to collect neural recordings specifically for research. The recording system will be disconnected at the completion of each research session. sEEG electrodes will be connected to the EMU's recording system for the duration of each participant's inpatient stay per standard of care.

The study team's recording equipment consists of the software required to present stimuli on MATLAB and record electrical signals from electrodes as well as behavioral responses from subjects. Therefore, no audio or visual recordings will be taken.

The risks and benefits of clinical procedures that are part of the patient's standard of care will be explained in a consent process separate from research activities. Electrode placement and recording are conducted strictly based on a patient's clinical needs and will not be dictated or manipulated by research. Participants will incur minimal additional risk by participating in the behavioral research task. Any risks involved will be explained and documented in the informed consent process and may include fatigue, boredom, or frustration. Research staff will ensure that participants and parents/guardians are aware that participation is entirely voluntary and may stop at any time. Every effort will be made to ensure patient comfort throughout study procedures.
